### If Yes to any of the above, do not randomize.

Was preoperative bowel prep administered?                      Yes                      No

Primary indication for surgery

- Adnexal mass
- Abnormal uterine bleeding (with or without fibroids)
- Fibroid uterus (without abnormal uterine bleeding)
- Pelvic organ prolapse
- Other (Please indicate) \_\_\_\_\_

Procedures performed

- Open abdominal hysterectomy
- Open sacral colpopexy
- Open surgery, other
- Vaginal hysterectomy
- Other vaginal only surgery
- Laparoscopic or robotic hysterectomy (including laparoscopic or robotic assisted vaginal hysterectomy)
- Laparoscopic or robotic sacral colpopexy
- Laparoscopic or robotic surgery, other
- Posterior colporrhaphy
- Burch urethropexy alone
- Other (Please indicate) \_\_\_\_\_

Estimated blood loss \_\_\_\_\_ ml

Surgery start time \_\_\_\_\_

Surgery end time \_\_\_\_\_

**Prunes Data Collection Sheet**  
**Data collected on post op day 3**

Day of discharge to home (if discharged)  
Time of discharge to home (if discharged)

1

2

3

---

# Prunes Data Collection Sheet

## Self administered survey

Have you had a bowel movement since surgery? Yes No

If Yes, When did you have your first bowel movement?

Date \_\_\_\_\_ Time \_\_\_\_\_

How *painful* was your first bowel movement?

Not at all painful 0    1    2    3    4    5    6    7    8    9    10 Very painful

Which picture best describes your bowel movement (Circle one number)?

1    2    3    4    5    6    7

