## 1.0 BACKGROUND AND HYPOTHESES

### 1.1 Background:

Postoperative constipation is among the most common complaints among women after gynecologic surgery. In the early postoperative period a temporary delay in gastrointestinal motility can be expected secondary to manual manipulation of bowel and medications including anesthesia and opiates. Postoperative constipation is a significant problem as return of bowel function is the most common reason for delayed hospital discharge after abdominal surgery. Without intervention, the average time to bowel movement after benign gynecologic and urogynecologic surgery is 4 days +/- 1.5 days. Delayed time to first bowel movement after surgery is often associated with patient discomfort and contributes to a delay in postoperative recovery.

The exact pathophysiology of delayed return of bowel function is unknown. Bayliss and Starling described the presence of inhibitory spinal reflexes acting on the bowel in 1899, which were later identified to be sympathetic inhibitory pathways in the autonomic nervous system. Sympathetic inhibition involves prevention of acetylcholine release from excitatory fibers in the myenteric plexus. The enteric nervous system has also been implicated as Holzer and Lippe suggested the role of Substance P, a neurotransmitter associated with pain. Bult et al. proposed that nitric oxide is the major inhibitory nonadrenergic noncholinergic neurotransmitter in the enteric nervous system. Hormones and neuropeptides such as vasoactive intestinal peptides, inflammation mediated by macrophages and neutrophils, general anesthesia and opioid narcotics may also contribute to the pathophysiology of delayed return to bowel function after surgery.

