### 3.6 Evaluation Post-Intervention:

1. All participants will record the date and time of, consistency of and pain associated with their first bowel movement, and answer whether they experienced secondary outcomes as described later.

2. Participants in the treatment arm will also log the number of prunes consumed each day.

2. Participants will be given a stamped and addressed envelope to return the data collection sheets in. Participants will receive a call from an investigator masked to the treatment allocation on postoperative day 3 inquiring about whether the participant has mailed the data collection sheets back. Those who do not answer will be called again the next day.

3. During the phone call, if the participant indicates any postoperative concerns, she will be instructed to contact the on call physician at the LAC+USC Ob/Gyn Triage.

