#### 10.0 CRITERIA FOR EVALUATION AND ENDPOINT DEFINITIONS

The outcome status of all eligible patients will be reported. All eligible patients who begin treatment will be included in the analysis.

Primary endpoints: Time to first bowel movement (in hours)

Secondary endpoints:

1. Stool consistency of the first bowel movement as classified by the Bristol Stool Scale (The stool types are categorical variables, and we will evaluate the differences in the frequencies of the responses by treatment status with a chi-square test)
2. Pain with bowel movement measured (Likert scale, and assessed using t-test or non-parametric methods as appropriate)
3. Satisfaction with bowel regimen (Likert scale, and assessed using t-test or non-parametric methods as appropriate)
4. Satisfaction with surgery overall (Likert scale, and assessed using t-test or non-parametric methods as appropriate)
5. Requirements for laxative (yes or no, assessed as categorical variables and evaluated by chi-square test)
6. Compliance with docusate (percentage of medications consumed, and assessed using t-test or non-parametric methods as appropriate)
7. Compliance with prunes (percentage of prunes consumed, and assessed using t-test or non-parametric methods as appropriate)

8. Adverse events of extreme bloating or flatulence (yes or no, assessed as categorical variables and evaluated by chi-square test)

Compliance with prune consumption will be defined as reported successful consumption of 2/3 of the assigned prunes.

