#### 13.0 STATISTICAL CONSIDERATIONS

The sample size of 63 participants per treatment group was calculated to detect a clinically significant mean difference in time to first bowel movement of 12 hours using a two-sample t-test with a standard deviation of 23.7 at 80% power and two-sided significance level of  $p=0.05$ . The sample size was inflated to 70 participants per group to account for an estimated 10% attrition rate.

Summaries of participant characteristics will be described by treatment arm. Participant characteristics will be presented as means and standard deviations for continuous variables and counts and percentages for categorical variables. Comparisons of baseline characteristics will be assessed using two-sample t-tests or the non-parametric corollary for continuous variables and chi-square test for categorical variables. The primary outcome, a comparison of the time to first bowel movement between the treatment and control groups, will be assessed using two-sample t-tests. The secondary outcome, pain at first BM, will also be evaluated using two sample t-tests.

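### A survey sheet can be returned before the first bowel movement and the visible text plans no re-contact, so the pain and stool-type tests may compare groups selected by the primary outcome

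*Combined protocol and SAP*

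**What the plan says.** - **Survey (Appendix III, English and Spanish).** The first item is "Have you had a bowel movement since surgery? Yes No". The date and time, pain and Bristol items that follow all refer to the first bowel movement, so a woman answering No has nothing to enter. The docusate and prune items cover days 1 to 3.
- **Section 3.6.** Every participant is expected to record the timing, consistency and pain of her first bowel movement. A masked investigator telephones "on postoperative day 3 inquiring about whether the participant has mailed the data collection sheets back". A woman who does not answer is called again the next day.
- **Section 9.0 calendar.** The mailed sheet appears under days 3 and 5, and the repeat call for women not reached is on day 5. This conflicts with 3.6, which implies day 4.
- **Section 6.3.** Each group gets a diary that is to include details of the first bowel movement. The diaries in Appendices IV and V are hourly grids for prunes and stool softener, with no field for a bowel movement.
- **Section 10.0.** Secondary endpoint 1 is "Stool consistency of the first bowel movement as classified by the Bristol Stool Scale", tested by chi-square. Pain is tested by t-test or a non-parametric method. All eligible patients who begin treatment are to be analysed.
- **Section 13.0.** "The secondary outcome, pain at first BM, will also be evaluated using two sample t-tests".
- **Section 1.1.** Without intervention, "the average time to bowel movement after benign gynecologic and urogynecologic surgery is 4 days +/- 1.5 days".

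**The concern.** The only planned contact comes on day 3, and the protocol's own background mean is 4 days. A woman who mails a No sheet around the time of that call has no pain score or stool type, and the visible text provides no step that obtains them later. Sections 10.0 and 13.0 give no rule for her.

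Whether a value exists then depends on time to first bowel movement, which is the primary outcome and the one prunes are expected to shorten. If prunes work, late women are missing more often from the control arm. The two tests would no longer compare the groups as randomised. If pain and hardness rise with delay, the late women who would show that benefit are the ones left out. A null result on pain or stool form could not then be separated from selective missingness.

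Analysing the primary endpoint as censored time would not help here. A time can be censored; a missing pain score or stool type cannot be treated that way.

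**Working it through.** **1. The plan's own figure.** Section 13.0 gives a "mean difference in time to first bowel movement of 12 hours", a "standard deviation of 23.7" and 63 per group "at 80% power and two-sided significance level" of 0.05.
- Normal approximation: 2 × (1.960 + 0.842)² × 23.7² / 12² = 61.2, so 62.
- Exact two-sample t-test: 62.2, so 63 (power 80.5%).
- Attrition: 63 / 0.90 = 70.

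Both stated sizes reproduce. No sample size or power is given for pain or stool type.

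**2. Inputs for the illustration.**
- Benefit of 12 h (13.0).
- SD of 23.7 h (13.0) or 36 h (1.1, reading ±1.5 days as an SD).
- Control mean of 96 h (1.1, a figure without intervention). Both arms receive docusate, so 72 h is also tried; that value is an assumption.
- Return at c = 72, 96 or 120 h, matching contacts on days 3, 4 and 5. This is an assumption, because no return date is set.
- Normally distributed times (assumption).

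**3. Formulas.** For an arm with mean μ and SD σ, let a = (c − μ)/σ.
- Share with a pain or stool value = Φ(a).
- Mean delay among women with a value = μ − σ·φ(a)/Φ(a).

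**4. One case in full** (c = 72, σ = 23.7).
- Control: a = (72 − 96)/23.7 = −1.013; share 15.6%; mean 96 − 23.7 × 1.535 = 59.6 h.
- Prunes: a = (72 − 84)/23.7 = −0.506; share 30.6%; mean 84 − 23.7 × 1.146 = 56.8 h.
- Delay difference kept: 2.8 h of 12 h, a loss of 77%.
- Of 63 per arm, about 10 controls and 19 prune women have values.

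**5. All cases.**

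| Control mean | Return | SD 23.7: share with value, control v prunes; hours kept; loss | SD 36: the same |
|---|---|---|---|
| 96 h | 72 h | 16% v 31%; 2.8; 77% | 25% v 37%; 3.2; 73% |
| 96 h | 96 h | 50% v 69%; 5.1; 58% | 50% v 63%; 4.8; 60% |
| 96 h | 120 h | 84% v 94%; 8.5; 29% | 75% v 84%; 7.0; 42% |
| 72 h | 72 h | 50% v 69%; 5.1; 58% | 50% v 63%; 4.8; 60% |
| 72 h | 96 h | 84% v 94%; 8.5; 29% | 75% v 84%; 7.0; 42% |
| 72 h | 120 h | 98% v 99%; 11.1; 7% | 91% v 95%; 9.3; 23% |

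If every woman waits for the event, all shares are 100% and the loss is zero.

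**6. Bias when prunes have no effect on pain.** Suppose pain correlates ρ = 0.3 to 0.5 with slow transit (assumption). The spurious difference in SD units is ρ × [φ/Φ in controls − φ/Φ in prunes]. In the case above with ρ = 0.5 it is 0.5 × (1.535 − 1.146) = 0.19. Over the three return times it is 0.04 to 0.20 SD for a 96 h mean and 0.01 to 0.15 SD for a 72 h mean. It runs against prunes, because that arm keeps more of its slower women. The type I error at a nominal 5% becomes about 5% to 10%.

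**7. Loss of information.** Take a pain effect of 0.506 SD (12/23.7, borrowed from the primary endpoint as an assumption). Power is Φ(0.506/√(1/n₁ + 1/n₂) − 1.96). With 63 per group it is 81%. With a control mean of 96 h it falls to 25-34% for return at 72 h, 56-58% at 96 h and 71-76% at 120 h.

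**The case against.** The strongest reply is that the protocol intends every first bowel movement to be recorded. Section 3.6 says so without limiting it to day 3, and 6.3 promises a diary for the details. The day-3 call sets no deadline, the calendar also shows the sheet under day 5, and the stool-softener diary runs to day 5. The consent pages were not part of the text reviewed and may contain return instructions.

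Much of this stands. It means that return on day 3 is a possibility and not a rule, and that the gap can be asserted only of the visible text. It does not close the gap. No visible instruction tells women to hold the sheet, the form provides for a No answer, the diaries lack the field, and the repeat call is only for women not reached the first time.

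A reader might infer that most of any benefit on pain or stool form would vanish. The documents do not support that. Losses of two thirds or more arise only with the earliest returns and a 96 h control mean, and they concern only benefit that acts through delay. Section 1.2 attributes the efficacy of prunes to fibre and to acids that reach the colon undigested. A direct effect on stool form would not be removed by this selection.

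A reader might also infer that the tests are uninterpretable. The bias in step 6 is modest; the loss of information is the larger cost.

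**Conclusion.** The concern holds as a gap in data collection and analysis for two secondary endpoints. Followed as written, the plan allows pain and Bristol type to be missing because of the primary outcome, and more often in controls if prunes work.

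The size cannot be fixed from the documents. Under normal times and a 12 h benefit, 29-77% of the delay difference is lost among women with values when the control mean is 96 h, and 7-60% when it is 72 h, for returns between 72 and 120 h. It is zero if every woman waits.

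The documents do not show that women will return sheets on day 3, so the upper end of the range should not be read as the expected loss. The change is worth making because it is cheap and the values cannot be reliably recovered afterwards.

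**What to change.** - **Section 3.6 and both language versions of the survey:** tell women to complete the first-stool items at the first bowel movement and to mail the sheet after it.
- **Follow-up call:** ask whether the first bowel movement has occurred. Make one further call to any woman whose sheet is marked No, to obtain date and time, pain and stool type. This call has to be added, because none exists for women already reached on day 3. It also recovers the primary time for the same women.
- **Sections 3.6 and 9.0:** reconcile the repeat call, which is on day 4 in one and day 5 in the other.
- **Sections 10.0 and 13.0:** report by arm how many women have no value because no bowel movement had occurred. If any remain, label the pain and Bristol tests as conditional on a bowel movement.
- **Optional sensitivity analysis:** a rank analysis of pain that places women without a stool worst. It mixes absence of a stool with pain, so it should not replace the main analysis. It should not be applied to Bristol type, which has no single worst end.

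Cost: one instruction on the form in each language, a short paragraph in the analysis section, and one extra short call for some women.

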### Bristol stool chart

Type 1		Separate hard lumps, like nuts (hard to pass)
Type 2		Sausage-shaped but lumpy
Type 3		Like a sausage but with cracks on its surface
Type 4		Like a sausage or snake, smooth and soft
Type 5		Soft blobs with clear-cut edges (passed easily)
Type 6		Fluffy pieces with ragged edges, a mushy stool
Type 7		Watery, no solid pieces, Entirely liquid

How satisfied were you with the treatments you received to help you with bowel movements after the surgery?

Not at all satisfied 0    1    2    3    4    5    6    7    8    9    10 Extremely satisfied

How satisfied were you with your surgery overall?

Not at all satisfied 0    1    2    3    4    5    6    7    8    9    10 Extremely satisfied

How many docusate did you take on day 1? \_\_\_\_\_

How many docusate did you take on day 2? \_\_\_\_\_

How many docusate did you take on day 3? \_\_\_\_\_

Did you use any laxatives? Yes No

If yes, what? \_\_\_\_\_

If yes, what day? \_\_\_\_\_

If in study group (prunes):

How many prunes did you eat on day 1? \_\_\_\_\_

How many prunes did you eat on day 2? \_\_\_\_\_

How many prunes did you eat on day 3? \_\_\_\_\_

**Prunes Data Collection Sheet**  
**Self administered survey – Spanish**

¿Ha tenido una evacuación intestinal desde la cirugía?  Sí  No

Si la respuesta es Sí, ¿Cuándo tuvo su primer movimiento intestinal?

Fecha \_\_\_\_\_ Hora \_\_\_\_\_

¿Cuán doloroso fue su primer movimiento intestinal?

Nada doloroso 0 1 2 3 4 5 6 7 8 9 10 Muy doloroso

¿Qué imagen describe mejor su movimiento intestinal (encierre en un círculo un número)?

1 2 3 4 5 6 7

**Bristol stool chart**

Type 1		Heces en bolas duras y separadas. Como frutos secos.
Type 2		Heces con forma alargada como una salchicha pero con relieves como formada por bolas unidas.
Type 3		Heces con forma alargada como una salchicha, con grietas en la superficie.
Type 4		Heces con forma alargada como una salchicha, lisa y blanda.
Type 5		Heces blandas y a trozos separadas o con bordes defractos.
Type 6		Heces blandas y a trozos separadas o con bordes pegados como mermelada o pure.
Type 7		Heces liquidas sin trozos solidos.

¿Cuán satisfecho estuvo con los tratamientos que recibió para ayudarle con los movimientos intestinales después de la cirugía?

Nada 0 1 2 3 4 5 6 7 8 9 10 Extremadamente  
satisfecho satisfecho

¿Qué tan satisfecho estuvo con su cirugía en general?

Nada 0 1 2 3 4 5 6 7 8 9 10 Extremadamente  
satisfecho satisfecho

¿Cuántos docusate tomó el día 1? \_\_\_\_\_

¿Cuántos docusate tomó el día 2? \_\_\_\_\_

¿Cuántos docusate tomó el día 3? \_\_\_\_\_

¿Utilizó algún laxante?  Sí  No

Si sí, ¿qué? \_\_\_\_\_

Si sí, ¿qué día? \_\_\_\_\_

Si en el grupo de estudio (ciruelas pasas):

¿Cuántas ciruelas comió el día 1? \_\_\_\_\_

¿Cuántas ciruelas pasas comiste el día 2? \_\_\_\_\_

¿Cuántas ciruelas comió el día 3? \_\_\_\_\_

## Appendix IV: Prune Diary

Mark on the chart below what time you ate a prune.

Marque en la tabla debajo de qué hora usted comió una ciruela pasa.

	Day 1	Day 2	Day 3
6am			
7am			
8am			
9am			
10am			
11am			
12noon			
1pm			
2pm			
3pm			
4pm			
5pm			
6pm			
7pm			
8pm			
9pm			
10pm			
11pm			
12midnight			
1am			
2am			
3am			
4am			
5am			

**Appendix V: Stool softener diary**

Mark on the chart below what time you took your stool softener medication.

Marque en la tabla debajo de qué hora tomó su medicación suavizante de heces.

	Day 1	Day 2	Day 3	Day 4	Day 5
6am					
7am					
8am					
9am					
10am					
11am					
12noon					
1pm					
2pm					
3pm					
4pm					
5pm					
6pm					
7pm					
8pm					
9pm					
10pm					
11pm					
12midnight					
1am					
2am					
3am					
4am					
5am
